**Create or insert table to describe the exclusion criteria and methods to ascertain them**

EXCLUSION CRITERIA	METHOD OF ASCERTAINMENT
1. Meets DSM IV criteria for bipolar disorder, schizophrenia or any psychotic disorder other than transient psychosis due to drug abuse. Substance Induced Mood Disorder with Hamilton Depression Scale score $\geq 15$ will be excluded. Patients with Major Depressive Disorder will be eligible to participate, provided they are in remission (Hamilton Depression Scale-25 Score < 8), whether receiving treatment or not.	MINI interview, self-report
2. History of allergic, dermatological, or adverse event related to oxytocin or desmopressin. Patient using oxytocin or vasopressin-based products cannot participate.	Self report
3. Chronic organic mental disorder, insufficient proficiency in English, or any condition or status (illiteracy) that would render an individual incapable of giving informed consent.	Psychiatric evaluation
4. Significant current suicidal risks, suicide attempt within the past year.	Psychiatric evaluation
5. Unstable physical disorders, which might make participation hazardous: hypertension (>140/90), hepatitis (patients with chronic	Medical evaluation

mildly elevated transaminase levels (2-3 X upper limit of normal will be considered acceptable if PT/PTT is normal), serum sodium (Na) < 133 mEq/L, renal failure (creat >2; BUN > 40. History of hyponatremia. Patients on medication (\*) (see partial list below) that may induce hyponatremia will not be excluded, provided no evidence of hyponatremia is found at screening.

6. Coronary vascular disease as indicated by history, or suspected by abnormal ECG. Electrocardiogram, medical history

7. Currently meets DSM-IV criteria for another substance dependence or abuse disorder other than nicotine, or alcohol. If alcohol dependent, must not be in need of detoxification. MINI, medical eval, utox

8. Participants who cannot comply with study procedures during the inpatient or outpatient abstinence induction (phase 1) will not proceed to phase 2. Study performance

9. Pregnancy, positive urine pregnancy test, or breastfeeding. Women who wish to participate must agree to use a method of contraception during the study and sign a written commitment to that effect, and submit to a urine pregnancy test every two weeks of phase 2 History, medical monitoring.

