**Type in the name(s) not found in the above list**

**Study Procedures**

**Describe the procedures required for this study**

**Design Overview:**

This is a 2 phases, 7-weeks, prospective, double-blind, placebo-controlled, randomized clinical trial of comparing intranasal oxytocin to placebo in cocaine-dependent patients. The principal aim of the study is to examine if intranasal oxytocin can reduce the relapse risk. Cocaine-dependent and control patients will be recruited through IRB-approved advertising in public media, and from the STARS clinic of the Division on Substance Abuse at the New York State Psychiatric Institute, and the Division on Substance Abuse at the Albert Einstein College of Medicine. Prior to the 6-week outpatient phase, cocaine-dependent patients will be required to become abstinent. To achieve this, patients will opt for either an inpatient or an outpatient approach. During the inpatient approach, patients will be hospitalized at the New York State Psychiatric Institute (5-South) for 7 days to establish abstinence, participate in the stress challenge over 2 separate days which evaluates baseline stress sensitivity, investigate if oxytocin can exert an acute effect on stress parameters, and begin on randomized medication (IN oxytocin 24 IU/day vs. IN placebo). There will not be a placebo lead-in.

Table 1 presents an overview of phase 1 for cocaine-dependent and control patients.

see up-loaded table 1.

---

Because of professional, personal, or financial reasons, some patients may choose *the outpatient abstinence-induction procedure*. During this week, patients will need to attend the clinic on three consecutive days and provide a negative urine toxicology for cocaine at each visit. Following this, they must complete all the study procedures prescribed in the in-patient Phase 1 procedure: essentially the stress challenges as described in section 4A3 below. If a patient cannot remain abstinent during this week, the patient will be offered another attempt to become abstinent during following week and complete the phase 1 procedures. If a patient cannot achieve abstinence during either week, then the inpatient phase will be mandatory for continued participation. If the patient cannot do this, we will offer referrals for treatment in another setting.

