**measurements are repeated at specified time points.**

5) After baseline stress testing is completed, begin randomized administration of intranasal Oxytocin 20 IU per day in the morning, for each remaining day of phase 1. This will serve also as an opportunity to train patients on how to administer intranasal solutions. The steps are as follows: 1) exhale through the nose, head bent forward; 2) while inhaling, spray once into one nostril; 3) repeat step 1 & 2 for the other nostril; 4) repeat steps 1 to 3 again to reach the daily dose of 24 IU of randomized medication. The patients will be instructed by a member of the research staff to ensure proper technique and optimal absorption of the medication. The Oxytocin solution is stable at room temperature for one month after being opened. Nonetheless, the manufacturer recommends that the bottle be kept refrigerated between uses and we will recommend this to the patients as well. Its stability should ensure that transportation to the clinic should not cause degradation, provided it is not exposed to extreme heat (> 100 Fahrenheit), direct sunlight, or frozen.

Phase 1, control participants.

The purpose of Phase 1 for control participants without psychiatric, medical, or addiction disorders is to test their stress sensitivity with the same procedure as cocaine-dependent patients. This is to study if stress dysregulation is more prevalent among cocaine users than normal controls, and to study if vasopressin-based stress mechanisms bear some specificity to the stress dysregulation observed in cocaine-dependent patients.

For control participants, the procedure will be carried out over two days as outpatients. They will be instructed to present themselves between 9 to 10 am on a testing morning, having eaten breakfast. A saline lock will be inserted, and a 2-hour habituation period will follow before testing begins at approximately 1 pm. The procedure will be the same as described for cocaine-dependent patients, and will be administered in counterbalanced order (**see above, stress procedures**). Completion of phase 1 ends their participation in this study.

Phase 1, week 1, cocaine-dependent patients, outpatient version.

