This procedure is based on our previous experience acquired during protocol NYSPI IRB 6013 (mifepristone study for cocaine dependence) with patients who cannot participate in the inpatient procedure. Over a period of 7 days, not counting Saturdays and Sundays, a participant will have to produce at least three consecutive cocaine negative urine toxicologies at daily visits. Once abstinence is established the phase 1 procedures begin (Table 1), with verification of negative toxicology before each testing day. Randomized medication will begin after completion of all the physiological tests.

---

If a urine toxicology test emerges positive for cocaine once Phase-1 procedures have begun, the testing will stop. The patient can then attempt another period of seven days to reach abstinence, complete the baseline testing, and begin randomized medication. If abstinence cannot be reached during this two-week window, the patient will be offered to carry out phase 1 as an inpatient. If the patient cannot participate as an inpatient, referrals to other treatment options will be offered.

Phase 2, outpatient phase, week 2 to 7, cocaine-dependent patients only

During this phase in which only cocaine-dependent patients participate, they will continue randomized medication while participating in a structured program to support and promote continuing abstinence and completion of the study.

For patients continuing at the STARS clinic and DOSA at Waters Place ([name]), the structure of the program during this phase will be as follows:

- 1: Patients continue to receive intranasal Oxytocin (24IU/day) vs. intranasal placebo. During their visits to either clinic, they will administer the randomized medication under supervision from a bottle kept at the clinic. Each witnessed administration will be recorded. Since they "self-administer" the medication, it can be witnessed by any member of the research team.

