4. Oxytocin: Oxytocin is used during labor and delivery to promote uterine contraction. In this instance, doses vary, but far exceed the daily dose of 24 IU/day used in this study. Administered intravenously as Pitocin, it can also lead to hyponatremia, arrhythmia, convulsions, chest pain, shortness of breath, confusion, swelling, headache, nausea/vomiting, cardiac arrhythmia. During their participation, control participants will receive 2 consecutive doses of IN oxytocin (40 IU in total) during phase 1. Cocaine-dependent patients receive 47 doses of IN oxytocin (940 IU) over a period of 7 weeks. No serious adverse events arose in a study during which 40 IU were administered daily for one week, then 80IU/day for another 7 weeks (Modabbernia et al., 2013). Feeling too relaxed, light-headedness, anxiety, clouded thinking, and nasal cavity irritation are the most common side effects reported in protocols approximating the one presented here (Rodrigues et al., 2009; Ditzen et al., 2009).
  
5. Another potential risk, especially for intranasal cocaine users, is whether the use of the intranasal approach would serve as a trigger for cocaine use. As this pharmacological approach has not been investigated before, this will be specifically queried for during clinic-based administration.
  
6. No data exists examining the risk of cocaine use is enhanced by concomitant intake of oxytocin. We

---

do not anticipate that it would increase the risk of cocaine use. As change in cocaine use is a main outcome of the study, evidence of increased cocaine use will be monitored closely.

7. The stress challenge may cause patients to experience cravings for cocaine. After each procedure, a gradual muscle relaxation procedure will be used to reduce these.
  
8. Vouchers could be exchanged for drugs, or their monetary value could serve as a trigger to procure cocaine. Expending vouchers is a major topic of the counseling during the study to promote a drug-free lifestyle.
  
9. The structured interviews, self-reports, and questionnaires should not pose a physical risk. Their disadvantage is the time to complete them. Our past experience using these measures indicates that patients find them acceptable.
  
10. The risk of the blood tests is the discomfort associated with venipuncture, and a possibility of slight bruising. For the stress challenge, a saline lock will be placed to avoid repeated venipuncture.
  

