
3.3 Compensation and data management.

For phase 1, control participants will receive \$150 for their participation; cocaine-dependent patients will receive \$20/day, or will receive \$150 if they complete the whole week. [During phase 2, cocaine-dependent patients accumulate vouchers for completing all study procedures (Bringing home bottle, assessments, study visits).] Each visit with all study procedures completed will earn them \$5. They can also earn \$20 for each week of consecutive and complete participation. Transportation costs are covered (\$5/visit). Total earnings can reach \$450. StudyTrack, a software system for clinical trials will be used for data management.

3.4 Statistical Analysis:

3.4.1. Outcome measures: PHASE 1: **Primary outcomes:** 1) secretion of ACTH (continuous measure of area from the concentration-time curve (AUC) using trapezoid method, pg/mL/min). 2) subjective rating of cocaine craving, stress, depression, anxiety (continuous) 3) difference in ACTH secretion between IN DDAVP (day 1) and IN OT prior to IN DDAVP (day 2) (continuous measure); 4) difference in subjective rating of cocaine

craving, stress, depression, anxiety between IN VP (day 1) and IN OT prior to IN DDAVP (day 2; continuous, controlled for last day of use before entering Phase 1); **PHASE 2: Primary outcome:** 1) maximum number of consecutive abstinent days (continuous measure) ; **Secondary outcome:** 1) cocaine using days (continuous). **Covariates/Predictor Variables:** demographics, age, gender; cocaine data (TLFB, 30 days; IN vs. smoked).

3.4.2. Sample size: In PHASE 1, we will enroll a total of 100 participants: 1) Cocaine group (COC): Cocaine-dependent patients seeking treatment (n=50); 2) Control group (CON): Healthy matched controls (n=50), each matched demographically (see 3.1.1). In PHASE 2, we will randomize the 50 COC patients into two groups: 1) Oxytocin group (OT), n=25; 2) Placebo group (PBO), n=25. An independent statistician will perform, and an independent pharmacist will implement the randomization. Individuals will be stratified by route of cocaine use. The randomization will be balanced in blocks of random size 2 and 4 to prevent compromise of the blind.

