3.4.3. Intent to Treat/ Dropouts and missing data: All primary analysis will be on Intent-to-Treat (ITT) sample, i.e. all subjects from COC and CON groups in Phase 1 (50 per arm) and all subjects randomized to OT and PBO groups in Phase 2 (25 per arm). [In Phase 1, we expect little attrition. Measures as described (3.4.1) will provide usable data after 2 days of measurements. For phase 2, we anticipate an attrition rate of 30%, leaving approximately 18 completers per arm.] If a patient drops out during Phase 2, the maximum number of consecutive abstinent days achieved in the trial will be considered as primary outcome. The inferences from analyses with missing data are considered valid provided that they are "missing at random" (Little and Rubin 1987). One can assume either parametric or semi-parametric models for missingness (Diggle and Kenward 1994; Kenward 1998; Liu et al 1999; Rotnitzky et al 1998). Inferences from various models of missingness provides a measure of the efficacy estimate from each models.

3.4.4. Significance testing and preliminary analyses: All tests for main effects will be performed at two-tailed significance $\alpha=5\%$. Before performing specific analyses (described below), we will examine all variables for outliers and normality. Demographic variables (ethnicity, gender, age) and baseline measures in the groups will be described in terms of means, standard deviations, proportions and 95% confidence intervals. The covariates (Section 3.4.1) will be included if they are found to affect outcome measures.

Hypotheses:

Primary Aim 1 [Phase 1]: The goal of primary aim 1 is to investigate the effect that both IN DDAVP and OT have on stress sensitivity. **Primary Aim 1a, hypothesis 1:** IN DDAVP will be associated with greater secretion of ACTH and subjective ratings in cocaine dependent patients compared to control patients. **Primary Aim 1b, hypothesis 2:** IN OT treatment will significantly reduce the secretion of ACTH and subjective ratings associated with IN DDAVP in cocaine dependent patients compared to control patients. The differences based on the outcomes specified in hypotheses 1 and 2 between the subjects in COC and CON groups will be examined using parametric or non-parametric matched sample test.

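### Randomised spray starts in Phase 1, but the SAP ties randomisation, the ITT set and the dropout rule to Phase 2, so patients dosed before Phase 2 have no clear place in the primary comparison

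*SAP*

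**What the plan says.** **Protocol.** The Design Overview says inpatients will, during the 7-day stay, complete the stress challenge "and begin on randomized medication (IN oxytocin 24 IU/day vs. IN placebo". Step 5 of the in-hospital Phase 1 procedure says that after stress testing staff will "begin randomized administration of intranasal Oxytocin 20 IU per day in the morning, for each remaining day of phase 1". For the outpatient version of Phase 1: "Randomized medication will begin after completion of all the physiological tests". The Phase 2 section then says of patients that "they will continue randomized medication while participating in a structured program". Exclusion criterion 8 for the cocaine-dependent sample reads: "Participants who cannot comply with study procedures during the inpatient or outpatient abstinence induction (phase 1) will not proceed to phase 2".

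**SAP.** Section 3.4.2: "In PHASE 2, we will randomize the 50 COC patients into two groups". Section 3.4.3 takes as the analysis set for the oxytocin comparison "all subjects randomized to OT and PBO groups in Phase 2 (25 per arm". For a patient who drops out during Phase 2, the longest abstinent run achieved is used. The same section expects little Phase 1 attrition and 30% in Phase 2, about 18 completers per arm. The Power Analysis paragraph again places randomisation in Phase 2.

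Two of the quoted protocol sentences give different daily amounts of spray. Those passages must be reconciled, but nothing below depends on which holds.

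**The concern.** An intent-to-treat set is defined by the moment of allocation. The two documents put that moment in different places, and a compliance condition lies between them. A patient could be allocated, take randomised spray for a day or two, leave or fail to comply, and be stopped from entering Phase 2. That patient has been randomised and treated, yet the SAP's set and its dropout rule are both worded for Phase 2.

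Such patients would be early failures, whom a relapse-prevention trial needs to count. The protocol's risk section lists nasal irritation, light-headedness and anxiety, and raises the spray itself as a possible trigger for cocaine use. Effects of the nasal route would fall on both arms, but effects of the drug need not. If early losses differed by arm and were left out, the comparison would no longer be between the groups that randomisation formed.

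**Working it through.** **1. When does randomised dosing start?** All three protocol passages on starting medication put it after the challenges and within the description of Phase 1. The Phase 2 text speaks of continuing it. Allocation must therefore come before Phase 2.

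The protocol's dose count agrees. In the risk section, item 4: "Cocaine-dependent patients receive 47 doses of IN oxytocin (940 IU) over a period of 7 weeks".
- Phase 2 days: 6 weeks × 7 = 42.
- Doses outside Phase 2: 47 − 42 = 5.
- Less one oxytocin challenge dose: 5 − 1 = 4 randomised doses before Phase 2.
- Less two challenge doses (the same item counts two for controls): 5 − 2 = 3.

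The exposed window is thus about 3 to 4 doses.

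**2. What value would such a patient get?** The dropout rule in SAP 3.4.3 covers Phase 2 only. The SAP's closing section, which works in weeks, treats a week with neither toxicology nor self-report as missing, so a patient who never enters Phase 2 would have six missing weeks. The protocol's Phase 2 item 11 counts missed visits as use, but it does so for the responder rating. No passage gives a primary-outcome value.

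**3. The plan's own power figure.** Inputs from the Power Analysis: 25 per arm, standardised effect 0.8, two-sided 5%. By the normal approximation, power = Φ(d√(n/2) − 1.96) = Φ(0.8 × √12.5 − 1.96) = Φ(0.868) = 80.7%. The noncentral t gives 79.1%. The stated 80% reproduces, so the sample-size arithmetic is not at issue.

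**4. Power if such patients are left out.** The documents give no rate, so 5% to 20% is assumed, equal in both arms.

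| Assumed loss | Left per arm | Power (normal) | Power (t) |
|---|---|---|---|
| 0% | 25 | 80.7% | 79.1% |
| 5% | 23.75 | 78.7% | 77.0% |
| 10% | 22.5 | 76.5% | 74.6% |
| 20% | 20 | 71.6% | 69.3% |

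**5. Bias if losses fall in one arm only.** This is a simulation under no drug effect: 20,000 trials, 25 per arm, t-test. The normal outcome is an assumption. In the first pair of columns the patients removed are the worst in the arm; in the second, the reason for leaving correlates 0.5 with outcome.

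| Removed from one arm | Shift (SD), worst | Type I error | Shift (SD), correlation 0.5 | Type I error |
|---|---|---|---|---|
| 1 | 0.08 | 6.6% | 0.04 | 5.2% |
| 2 | 0.15 | 9.4% | 0.08 | 5.8% |
| 3 | 0.21 | 13.4% | 0.11 | 7.0% |

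Equal losses of the same kind in both arms give no expected shift in the difference.

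**The case against.** The strongest reply is that the SAP sentence may not restrict anything. It uses the phase names to label two comparisons, cocaine versus control in Phase 1 and oxytocin versus placebo in Phase 2, and it says all randomised subjects. SAP 3.4.2 randomises the same 50 patients it enrolled. On that reading everyone allocated is in the set. The protocol's Lay Summary also has patients entering the randomised trial after abstinence induction. This stands as a possible reading. The text does not settle it, and it still leaves the patient in question without an outcome value.

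Second, most of the Phase 1 hurdle comes before any randomised dose. On the outpatient route, three negative toxicologies, a negative test before each testing day and all challenges come first. On the inpatient route, abstinence is controlled and baseline stress testing is complete before dosing. This also stands. What remains after dosing is the general compliance clause, over a few days.

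A reader might infer that the run-in as a whole acts as a filter after randomisation, or that the reported comparison has been distorted. The documents support neither. Nor does the 15 versus 11 split of the 26 patients reported as randomised show omissions. With blocks of 2 and 4 and two route strata (an assumption), a gap of 4 is the largest possible and rare, about 0.4% in simulation. More strata or other causes could explain it.

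**Conclusion.** The protocol and SAP conflict on when randomisation happens, and the SAP's analysis set and dropout rule follow the later date. On the literal reading, a patient allocated and dosed late in Phase 1 who does not proceed is outside the primary comparison. On the generous reading the patient is inside it with nothing to analyse. Either way the rule is incomplete at the point where intent-to-treat has to be exact.

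The size is limited. The window is about 3 to 4 doses, the SAP expects little Phase 1 attrition, and no such loss is documented. The power cost is about 2 to 9 percentage points at an assumed 5% to 20% loss (80.7% to 78.7% or 71.6%). Bias depends on losses differing by arm. With 1 to 3 patients lost from one arm only, type I error would be 5.2% to 7.0% if leaving is moderately related to outcome, and 6.6% to 13.4% in the extreme case. These rest on assumed losses and a normal outcome. They show that a few patients could matter, not that they did.

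**What to change.** In SAP 3.4.2 and 3.4.3:

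1. Reconcile the time of randomisation with the protocol, at or before the first randomised dose. Bring the Power Analysis wording into line.
2. Define the intent-to-treat set as every patient allocated to an arm, whether or not they enter Phase 2.
3. Give allocated patients who never enter Phase 2 a primary-outcome value, for example a Phase 2 abstinent run of 0, with a sensitivity analysis under another choice.
4. Report the number of such patients and their reasons by arm. Results already appear in the SAP's closing section, so this count is the most immediate need. If it is zero in both arms, the reported comparison is unaffected.

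Exclusion criterion 8 need not change. It can stay as an operational rule, because who stays in the analysis is a separate matter from who continues in the study.

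The cost is a few sentences and one line in the participant flow. The downside is that a few zero-run patients may enter the primary analysis and make the estimate slightly less favourable.

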Study Assessments: (Table 1). **Physiological tests:** 1) *urine toxicology:* this will be estimated qualitatively at every visit by dipstick (Iscreen™, 9 drugs) which indicates the presence of cocaine, amphetamine, metamphetamine, cannabis, methadone, morphine, oxycodone, barbiturate, benzodiazepine. 2) *stress sensitivity testing:* as outlined in table 2, it is performed on two separate days, [in counterbalanced order.] Day 1: an endocrine challenge with IN DDAVP 80IU (de Goeij et al., 1991). After establishing baseline ACTH secretion, serum samples are taken at time points extending to 90 minutes. The DDAVP challenge is also repeated at the end of phase 2, to see if ACTH secretion is affected by 6 weeks of IN OT administration. Day 2 tests if pretreatment with IN OT treatment can acutely dampen the effect of DDAVP on ACTH secretion. After baseline is measured before and after IN OT, serum samples for ACTH are taken at time points extending to 90 minutes. Serum samples are spun, frozen at -20 Celsius, packed in dry ice, and shipped to the Nathan Kline Laboratory in Orangeburg, NY. 3) Medical monitoring: week 2,4,6: Na, K, Cl, CO3, spot cortisol, β-HCG for women. **Clinician Interviews:** 1) TLFB (Litten and Allan, 1992; baseline, each visit in phase 2). This is an adaptation of the alcohol TLFB, which estimates cocaine use in the past 30 days at baseline, and is then repeated at every visit with the aid of a calendar to obtain a day-by-day registry of cocaine use during phase 2. 2) CGI-O, (Guy, 1976; baseline, weekly during phase 2) the severity and improvement scales measure the overall clinical status of the subject and change from baseline. 3) BAS (Chaplin et al., 2010). This scale is used during stress sensitivity testing. Research staff rate participants on 13 items of behavior relating to arousal during the stress challenge. 4) Adverse event form is a check-list of side effects experienced by participants; 5) HamD, (Williams, 1988; baseline, each wk in phase 2). Estimates 25 depression symptoms. **Self reports:** 1) PSS (Cohen et al., 1983; baseline, weekly during phase 2) measures monthly situations in a subject's lives deemed stressful. Ten questions are scored between 0 (never) to 4 (very often). Modified, it will be administered weekly during phase 2, [and will include a open-ended question inquiring about any adverse life event in the past week.] 2) *Subjective ratings of cocaine craving, depression, anxiety, stress during stress testing (Likert scale 0 to 10, 10 = worse), performed during stress sensitivity testing.* 3) CCS (Weiss et al., 1997) 3-item questionnaire rating cravings for cocaine on a scale of 0 (none) to 9 (Strong).

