Primary Aim 2 [Phase 2]: The goal of primary aim 2 is to investigate the effect of OT on cocaine use after abstinence induction. **Primary Aim 2, hypothesis 1:** Cocaine-dependent patients receiving IN OT will display significantly more days of consecutive abstinence after abstinence induction compared with IN placebo at the end of the study. The effect of IN OT treatment (based on groups) on the primary outcome (maximum number of consecutive abstinence days for each patient) will be analyzed using generalized linear models (PROC GLIMMIX in SAS®) with main effect of randomization assignment (OT vs. PBO).

Secondary Hypotheses: We will examine the feasibility, safety, tolerability, and potential efficacy of IN OT for relapse prevention in cocaine dependence. 2.1): Cocaine-dependent patients receiving IN OT who complete all 6 weeks of phase 2 will tally fewer cocaine using days than placebo patients who complete all 6 weeks. 2.2): Cocaine-dependent patients receiving OT who relapse will tally fewer cocaine using days than patients receiving placebo who relapse. Regression analysis will be implemented using those who complete (2.1) and those who relapse (2.2) to test the effect of OT on the secondary outcome (cocaine using days).

Exploratory Aims: We will investigate a) if the acute reduction in stress sensitivity with IN OT in Phase 1 or at the end of Phase 2 (repeat IN DDAVP challenge) is associated with a greater number of days of continued abstinence from cocaine in Phase 2; b) if there are gender effects on the primary outcomes.

Power Analysis: **Primary aim 1:** With 50 cocaine dependent subjects and 50 matched controls, we have 50 matched pairs which give us at least 80% power to detect a significant difference between groups using 2-sided hypothesis test at a 5% level of significance for an effect size $\geq .41$. This is considered a small/medium effect size (Araya et al., 2006; Simeon et al., 2011), which are reasonable to expect based on the existing literature. **Primary aim 2:** In Phase 2, we randomize 50 participants into 2 groups (25 in PBO and 25 in OT). The comparison will achieve at least 80% power (testing 2-sided hypothesis of difference at 5% significance) when detecting an effect size ≥ 0.8 . This is a medium effect size that we based on existing relapse studies in cocaine dependence (Back et al., 2010).

Primary outcome:

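### Phase 1 has ten primary variables at 5% each and no rule saying whether all or any must differ, so neither the error rate nor the stated 80% power is fixed

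*SAP*

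**What the plan says.** SAP 3.4.1 (Outcome measures) lists four numbered primary outcomes for Phase 1:

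1. "secretion of ACTH (continuous measure of area from the concentration-time curve (AUC) using trapezoid method"): one variable.
2. "subjective rating of cocaine craving, stress, depression, anxiety (continuous"): four variables.
3. "difference in ACTH secretion between IN DDAVP (day 1) and IN OT prior to IN DDAVP (day 2"): one variable.
4. The same between-day difference for each of the four ratings: four variables.

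That makes 1 + 4 + 1 + 4 = 10. SAP 3.4.4 sets one significance level for everything: "All tests for main effects will be performed at two-tailed significance" of 5%.

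Hypothesis 1 in SAP 3.4.4, which also stands in the Protocol under Specific Aims and Hypotheses, reads: "IN DDAVP will be associated with greater secretion of ACTH and subjective ratings in cocaine dependent patients compared to control patients". Hypothesis 2 has the same form for the effect of oxytocin. Both are tested by a matched-sample comparison of cocaine-dependent and control participants.

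The SAP's Power Analysis claims at least 80% power with 50 matched pairs, "using 2-sided hypothesis test at a 5% level of significance for an effect size" of 0.41 or more. That describes a single unadjusted test.

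Neither document gives a lead outcome, a composite of the ratings, a testing order, an adjustment, or a rule for declaring either hypothesis supported.

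**The concern.** Primary Aim 1 rests on two hypotheses with five outcomes each. Without a decision rule, a mixed result, such as ACTH unchanged but one rating different, can be read as success or as failure, and the choice can be made after the data are seen. The two natural readings have different operating characteristics, and neither matches a 5% error rate together with 80% power.

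The ratings add further freedom. ACTH has a defined summary measure, but the ratings are repeated over the test session and have none. The list of ratings also varies: craving, stress, depression and anxiety in the SAP; anxiety, restlessness and craving in the Protocol's description of the stress challenge; craving and agitation in the Protocol's Assessment Instruments.

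**Working it through.** **Inputs.** From the SAP: 50 matched pairs, effect size 0.41, two-sided 5%, five outcomes per hypothesis, ten in all. Assumed: a common correlation ρ among the test statistics, varied from 0 to 0.9.

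**Step 1: the plan's own figure.** For a paired t-test, the noncentrality is 0.41 × √50 = 2.90 and the critical value on 49 degrees of freedom is 2.01. The noncentral t distribution gives power of 81.1%, so the stated 80% is right for one test.

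**Step 2: any one outcome is enough, and nothing truly differs.** With k independent tests the chance of at least one false positive is 1 − 0.95^k:

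- k = 5: 1 − 0.95^5 = 22.6%
- k = 10: 1 − 0.95^10 = 40.1%

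With common correlation ρ it is 1 − E[{Φ((1.96 − √ρ·U)/√(1−ρ)) − Φ((−1.96 − √ρ·U)/√(1−ρ))}^k], where U is standard normal.

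**Step 3: all five outcomes must be significant.** The false-success rate cannot exceed 5%. If every outcome truly has effect size 0.41 and the tests are independent, power per hypothesis is 0.811^5 = 35.1%. With correlation (normal approximation, marginal power held at 81.1%) it is E[{1 − Φ((1.96 − m − √ρ·U)/√(1−ρ))}^5], with m = 1.96 + Φ⁻¹(0.811).

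| ρ (assumed) | Any of 5: false positive | Any of 10: false positive | All 5: power |
|---|---|---|---|
| 0 | 23% | 40% | 35% |
| 0.3 | 21% | 35% | 46% |
| 0.5 | 18% | 29% | 53% |
| 0.7 | 15% | 21% | 61% |
| 0.9 | 10% | 13% | 70% |

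**Step 4: other counts, tests independent.** Taking the four numbered items as four tests gives 1 − 0.95^4 = 18.5%. The Protocol's shorter rating lists give eight tests (1 − 0.95^8 = 34%) or six (1 − 0.95^6 = 26%).

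**Step 5: direction.** The hypotheses are directional. Counting only false positives in the predicted direction, five independent tests give 1 − 0.975^5 = 12%, against 2.5% for one test.

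**Step 6: cost of alternative repairs, at effect size 0.41 and 50 pairs.**

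- Bonferroni over ten tests (0.005 each): power 49%.
- Bonferroni over two ACTH tests (0.025 each): power 72%.
- Two ACTH tests in fixed order at 5%: power to pass both is 0.811² = 66% if independent, and about 73% at correlation 0.7.
- One ACTH test per hypothesis at 5% with no order: power 81% for each.

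**The case against.** A reader might infer that the plan lets one significant rating out of eight carry the primary claim. It does not say so. Read literally, joining ACTH and the ratings with a conjunction asks for both, and the false-success rate is then at most 5%. That objection stands: the defect is an unstated rule, not a stated bad one. But the literal reading does not rescue the plan, because the stated 80% power then fails.

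A reader might also take 40%, or a range such as 21–40%, as the trial's false-positive rate. Those figures need the any-outcome reading, no true effect on any of the ten variables, pooling of two separately stated hypotheses, and correlations no higher than about 0.7. The documents supply none of these, so the per-hypothesis figures are the fairer summary.

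Three further objections have some force:

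- The Protocol's Lay Summary calls the study a preliminary investigation whose main outcome is consecutive days of abstinence, and Phase 2 has one primary outcome. That limits the weight of the point. Still, Phase 1 is labelled Primary Aim 1.
- The Lay Summary measures the challenge by ACTH and self-report together, so demoting the ratings is a choice. It has support in the documents: the SAP's Study Assessments describe both test days in terms of ACTH, and the Protocol times testing to make ACTH changes easier to detect.
- A fixed testing order would control error across both hypotheses, but it would make the oxytocin question depend on a cocaine-versus-control difference, a dependence the plan never states, and would lower power for hypothesis 2.

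**Conclusion.** The point holds as a gap with consequences, worth correcting but not fatal. Under the any-outcome reading, the false-positive chance is about 10–23% per hypothesis, or 13–40% over all ten variables, if nothing truly differs. Under the all-outcomes reading, power per hypothesis is about 35% with independent tests and stays below the stated 80% at every correlation examined. All of these assume a common correlation that the documents do not give. The power figures also assume effect size 0.41 on every outcome and 50 complete pairs. The plan's single-test power calculation is itself correct.

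**What to change.** In SAP 3.4.1 and 3.4.4:

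- For hypothesis 1, name ACTH area under the curve after desmopressin as the only primary outcome.
- For hypothesis 2, name the difference in ACTH area under the curve between the two conditions as the only primary outcome.
- Test each at two-sided 5% with no fixed order, so that the stated 80% power applies to each hypothesis.
- Move all ratings to secondary status and report them with confidence intervals.

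The cost is wording only, with no extra participants. The ratings lose primary status, and no error control is claimed across the two hypotheses (at most 1 − 0.95² = 9.75% if the tests are independent and neither effect exists). The SAP should say so.

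The SAP's closing Primary outcome section already reports a Phase 2 result, and the documents do not say whether Phase 1 has been analysed. If those data have been examined, label the choice of ACTH as post hoc and report all ten results.
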